7.1. Discontinuation of Study Intervention

When necessary, a participant may be permanently discontinued from LY3209590 or insulin degludec. If so, the participant will remain in the study and follow procedures for remaining study visits, as shown in the SoA.

Participants who stop LY3209590 or insulin degludec permanently will receive another non-study basal insulin (see Section 6.6.1). The new insulin will be recorded on the CRF.

A participant should be permanently discontinued from LY3209590 or insulin degludec if

- the participant becomes pregnant during the study
- the participant requests to discontinue intervention
- the participant is diagnosed with an active or untreated malignancy, except for successfully treated basal or squamous cell skin carcinoma
- the participant has not taken insulin degludec for more than 21 consecutive days or missed more than 3 consecutive doses of LY3209590, or
- in the opinion of the investigator, the participant should permanently discontinue LY3209590 or insulin degludec for safety reasons.

7.1.1. Liver Chemistry Stopping Criteria

The study intervention should be interrupted or discontinued if 1 or more of these conditions occur.

Elevation	Exception
ALT or AST >8x ULN	
ALT or AST >5x ULN for more than 2 weeks	
ALT or AST >3x ULN and either TBL >2x ULN or INR >1.5	In participants with Gilbert's syndrome, doubling of direct bilirubin should be used for intervention interruption or discontinuation decisions rather than TBL >2x ULN.
ALT or AST >3x ULN with the appearance of fatigue, nausea, vomiting, right upper quadrant pain or tenderness, fever, rash, and/or eosinophilia (>5%)	
ALP >3x ULN, when the source of increased ALP is the liver	
ALP >2.5x ULN and TBL > 2x ULN	In participants with Gilbert's syndrome, doubling of direct bilirubin should be used for intervention interruption or discontinuation decisions rather than TBL >2x ULN.

ALP >2.5x ULN with the appearance of fatigue, nausea, vomiting, right upper quadrant pain or tenderness, fever, rash, and/or eosinophilia (>5%)	
---	--

Resumption of the study intervention can be considered only in consultation with the Lilly-designated medical monitor and only if the liver test results return to baseline and if a self-limited, non-intervention etiology is identified.

7.1.2. Hypersensitivity Reactions

If the investigator determines that a systemic hypersensitivity reaction has occurred related to study intervention administration, the participant may be **permanently discontinued** from the study intervention, and the sponsor's designated medical monitor should be notified.

If the investigator is uncertain about whether a systemic hypersensitivity reaction has occurred and whether discontinuation of study intervention is warranted, the investigator may consult the sponsor.

7.1.3. Temporary Discontinuation of LY3209590 or Insulin Degludec

Criteria for temporary discontinuation of LY3209590 or insulin degludec

The investigator may temporarily interrupt study treatment, due to an AE, clinically significant laboratory value, hospital visits, travel, or shortage of study treatment supply.

This will be allowed for up to 3 consecutive weeks for degludec or 3 consecutive doses for LY3209590. During this time, non-study insulins may have been used. This information should be documented by the investigator.

Guidance when temporary discontinuation of LY3209590 or insulin degludec occurs

Every effort should be made by the investigator to maintain participants in the study and to restart LY3209590 or insulin degludec promptly, as soon as it is safe to do so.

Participants will continue their study visits and follow up according to the SoA.

Participants should resume the dose prescribed before the temporary dosing interruption at the discretion of the investigator.

Recording temporary discontinuation of LY3209590 or insulin degludec

The dates of LY3209590 or insulin degludec interruption and restart must be documented in source documents and entered on the CRF.

Participant noncompliance should not be recorded as interruption of LY3209590 or insulin degludec on the CRF.

7.2. Participant Discontinuation/Withdrawal from the Study

Discontinuation is expected to be uncommon.

A participant may withdraw from the study:

- at any time at the participant's own request
- at the request of the participant's designee (for example, parents or legal guardian)
- at the discretion of the investigator for safety, behavioral, compliance, or administrative reasons
- if enrolled in any other clinical study involving an investigational product, or enrolled in any other type of medical research judged not to be scientifically or medically compatible with this study
- if the participant, for any reason, requires treatment with a therapeutic agent that is prohibited by the protocol and has been demonstrated to be effective for treatment of the study indication. In this case, discontinuation from the study occurs prior to introduction of the new agent, and
- if a study participant is diagnosed with any type of diabetes mellitus other than T1D.

At the time of discontinuing from the study, if possible, the participant will complete procedures for an early discontinuation visit and post-treatment follow-up, if applicable, as shown in the SoA.

If the participant has not already discontinued the study intervention, the participant will be permanently discontinued from the study intervention at the time of the decision to discontinue the study.

If the participant withdraws consent for disclosure of future information, the sponsor may retain and continue to use any data collected before such a withdrawal of consent.

If a participant withdraws from the study, the participant may request destruction of any samples taken and not tested, and the investigator must document this in the site study records.

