To investigate the effect of LY3209590 compared with insulin degludec on other measures of efficacy, safety, and patient-reported outcomes	
Efficacy
 
 • Percentage of participants achieving HbA1c < 7% at Weeks 26 and 52 • Percentage of participants achieving HbA1c \leq 6.5% at Weeks 26 and 52 • Change from baseline to Weeks 26 and 52 in fasting serum glucose as measured by central laboratory
	
Safety
 
 • Rate and incidence of Level 2 hypoglycemia events during treatment period • Rate and incidence of Level 3 hypoglycemia events during treatment period • Incidence of positive treatment-emergent antibody of LY3209590

	
Patient-reported outcomes
 
 Frequency of responses to “Basal Insulin Experience: Likelihood of incorporating into routine” at Weeks 26 and 52 Frequency of responses to “Basal Insulin Experience: Preference” at Weeks 26 and 52 Change in EQ-5D-5L from baseline to Weeks 26 and 52
To characterize the PK/PD of LY3209590	
 LY3209590 PK and concentration response relationships to key safety and efficacy measures.

Abbreviations: CGM = continuous glucose monitoring; DTSQ = Diabetes Treatment Satisfaction Questionnaire; HbA1c = hemoglobin A1c; PK/PD = pharmacokinetics/pharmacodynamics; SF-36 = Short Form-36 Version 2 Health Survey Acute Form; SMBG = self-monitoring of blood glucose; T1D = Type 1 diabetes.

Primary estimand

United States registration

The primary clinical question of interest is

What is the treatment difference between LY3209590 and insulin degludec in HbA1c change from baseline after 26 weeks of treatment, in study eligible participants with T1D treated with MDI therapy, regardless of treatment discontinuation for any reason and regardless of initiation of rescue medication?

Treatment regimen estimand attributes

This table describes the treatment regimen estimand attributes.

Treatment Regimen Estimand Attributes	Description
Population	Targeted study population (see table in Section 9.2).
Endpoint	HbA1c change from baseline to Week 26.
Remaining intercurrent events	None. The 2 intercurrent events, treatment discontinuation for any reason and initiation of rescue medication, are both addressed by the treatment condition of interest attribute.
Treatment condition	The randomized treatment regardless of treatment discontinuation and use of rescue medications.

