6.1.2. Background Therapy

For patients with T1D, standard of care stipulates treatment with both basal and bolus insulin. In this study, participants will be treated with LY3209590 or insulin degludec as study basal insulin intervention and insulin lispro as prandial bolus background therapy.

Insulin lispro is being used to standardize the prandial insulin therapy.

6.1.3. **Rescue Therapy for Management of Participants with Severe, Persistent Hyperglycemia during the Treatment Period**

Participants in this clinical trial will be treated with basal insulin, that is LY3209590 or insulin degludec, in combination with prandial insulin lispro. Correction doses of insulin lispro can also be used.

If a participant develops severe, persistent hyperglycemia after randomization, based on meeting one of the criteria in this table, and in the absence of intercurrent cause of the hyperglycemia, rescue therapy with an additional therapeutic intervention should be considered.

Average Fasting Glucose over 2-week Period	Timing of events
>270 mg/dL (15 mmol/L)	Weeks 12 to 16 (from Visit 15 until Visit 17)
>240 mg/dL (13 mmol/L)	Weeks 16 to 20 (after Visit 17 until Visit 19)
>200 mg/dL (11 mmol/L)	Weeks 20 to 52 (after Visit 19 until Visit 29)

Investigators should first confirm that the participant is fully compliant with the assigned therapeutic regimen and that the participant does not have an acute condition causing severe hyperglycemia. If study basal and prandial insulin therapy is fully optimized, the investigator will decide, in consultation with the participant, on an appropriate intensification of insulin therapy after considering relevant clinical criteria. Participants who require a new non-study basal insulin intervention as rescue therapy for hyperglycemia management must discontinue study basal insulin therapy (LY3209590 or insulin degludec). The participant will remain in the study and follow procedures for the remaining study visits.

The investigator should ensure that the participant met the criteria for severe or persistent hyperglycemia before initiating rescue medicine and document this in the source files.

6.2. **Preparation, Handling, Storage, and Accountability**

The investigator or designee must confirm appropriate storage conditions have been maintained during transit for all study intervention received and any discrepancies are reported and resolved before use of the study intervention.

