9.1. Statistical Hypotheses

Primary hypothesis

The primary objective of this study is to test the hypothesis that LY3209590 is noninferior to insulin degludec on glycemic control as measured by change in HbA1c from baseline to Week 26 (Visit 22) in adults with T1D currently on basal-bolus insulin.

The null hypothesis (H_0) is the difference between LY3209590 and insulin degludec in the change in HbA1c from baseline to Week 26 (Visit 22) is greater than the NIM.

The NIMs of 0.4% and 0.3% will both be tested to meet different regulatory requirements. The 2-sided 95% CI will be used for testing the noninferiority.

Secondary hypotheses

The key secondary (multiplicity adjusted) objectives are to test the hypotheses that LY3209590 is superior to insulin degludec with respect to

- change in HbA1c from baseline to Week 26 (Visit 22)

H_0 : the difference (LY3209590 – insulin degludec) ≥ 0.0

- time in glucose range between 70 and 180 mg/dL (3.9 and 10.0 mmol/L) inclusive measured by CGM 4 weeks prior to Week 26 (Visit 22)

H_0 : the difference (LY3209590 – insulin degludec) ≤ 0.0

- the event rate of nocturnal hypoglycemia (<54 mg/dL [3.0 mmol/L] or severe) during treatment period up to Week 52 (Visit 29)

H_0 : the relative event rate (LY3209590 vs. insulin degludec) ≥ 1

These hypotheses and the primary hypothesis will be tested using a strategy to control the overall Type I error (see Section 9.1.1).

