9.1.1. Multiplicity Adjustment

A graphical approach (Bretz et al. 2009, 2011) for multiple comparisons will be used to ensure the strong control of overall Type I error rate for testing the primary and key secondary (multiplicity adjusted) objectives.

The overall significance level (α) will be set to 0.05. The total α will be used for the primary objective first, then the α will be allocated and transitioned to key secondary objectives once the primary objective is met. The testing procedure and α allocation will be established according to the clinical importance and statistical power of the endpoints in this study population.

The details of graphical testing scheme will be described in the SAP.

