9.5. Sample Size Determination

Approximately 670 participants will be randomized to LY3209590 and insulin degludec in a 1:1 ratio. With the assumption of 15% dropout at Week 26, approximately 284 and 284 participants will complete 26 weeks of treatment on LY3209590 and insulin degludec, respectively.

The primary objective of this study is to test the hypothesis that LY3209590 is noninferior to insulin degludec on glycemic control as measured by change from baseline to Visit 22 (Week 26) in HbA1c in participants with T1D currently basal-bolus insulin.

Assuming an NIM of 0.4%, no true difference between treatment groups, and an SD of 1.1%, 568 completers (284 on LY3209590 and 284 on insulin degludec) will provide at least 99% statistical power to show noninferiority between LY3209590 and insulin degludec using the upper limit of a 2-sided 95% CI (LY3209590 – insulin degludec). This sample size also has at least 90% statistical power to show noninferiority between LY3209590 and insulin degludec using a 0.3% NIM at Week 26.

The 568 completers will provide 90% statistical power to demonstrate the superiority (LY3209590 vs. insulin degludec) of change in HbA1c from baseline to 26 weeks (assuming an SD of 1.1% and true mean difference is -0.3%) using the alpha of 0.05.

The 568 completers will provide at least 99% statistical power to show the superiority of the percentage of time in glucose range between 70 and 180 mg/dL (3.9 and 10.0 mmol/L) inclusive measured by CGM 4 weeks prior to Week 26 between LY3209590 and insulin degludec (assuming an SD of 10% and true mean difference is 5%) at alpha = 0.05.

The 568 completers will provide 80% statistical power to show the superiority of the event rate of clinically significant nocturnal hypoglycemia (<54 mg/dL [3.0 mmol/L] or severe) during treatment phase up to Week 52 (assuming event rate of 3.37 [SD = 7.13] and 4.87 [SD = 7.13] events per participant per year for LY3209590 and insulin degludec, respectively) using a negative binomial distribution at alpha = 0.05.

10. Supporting Documentation and Operational Considerations

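### Protocol 7.2 takes participants out of the study before a prohibited effective agent starts, which conflicts with the remain-in-study rules for non-study basal insulin and with a US estimand defined regardless of rescue

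*Protocol*

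**What the plan says.** Protocol 7.2 lists circumstances in which a participant may leave the study. One is needing a therapeutic agent that the protocol prohibits and that is known to work for the study indication. For that item the text adds: "In this case, discontinuation from the study occurs prior to introduction of the new agent". The section does not refer to 6.1.3, 6.8 or 7.1 and makes no exception for them.

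Protocol 6.8 prohibits every oral or injectable diabetes medication except study insulins. The one item labelled as an exception is short-term non-study insulin during a temporary interruption (7.1.3). A Note under the same bullet covers rescue with non-study basal insulin: study basal insulin stops and the participant stays in the study.

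Protocol 6.1.3 says the same of rescue with a new non-study basal insulin: "The participant will remain in the study and follow procedures for the remaining study visits". Protocol 7.1 covers permanent discontinuation of study basal insulin for any reason: "If so, the participant will remain in the study and follow procedures for remaining study visits". It adds that these participants move to another non-study basal insulin.

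For US registration the primary estimand is the treatment-regimen estimand. Protocol section 3 gives its treatment condition as "The randomized treatment regardless of treatment discontinuation and use of rescue medications". EAS1 (Protocol 9.2, SAP 3) keeps all measurements whatever treatment was taken. SAP 1.2 expects HbA1c to be collected after permanent discontinuation of study intervention.

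SAP 4.3.2 imputes missing Week 26 HbA1c from retrieved dropouts: participants who stopped study treatment before Week 26 but were still measured then. If either arm has fewer than 8, or the model fails to converge, return-to-baseline multiple imputation is used.

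**The concern.** A participant who moves permanently to a non-study basal insulin fits two sets of instructions. The general prohibition in 6.8, taken with 7.2, ends study participation before the new insulin starts. Sections 6.1.3, 6.8 (Note) and 7.1 keep the participant in the study for the remaining visits. Because 7.2 says nothing about the other three, sites could act differently.

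The treatment-regimen estimand needs HbA1c at Week 26 whatever has happened to treatment. A participant withdrawn under 7.2 has no Week 26 value. A value from an early discontinuation visit would not replace it, because SAP 4.1 uses the planned Week 26 measurement or an unplanned one on the same visit day. If that participant had stopped study basal insulin, the loss counts twice: one more value to impute, and one fewer retrieved dropout to impute from. The key secondary time-in-range analysis and the Week 52 HbA1c analysis under this estimand use the same imputation approach.

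The efficacy estimand is hardly exposed, since EAS2 already cuts data off at rescue or shortly after the last study dose.

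**Working it through.** **Step 1. The sections side by side.**

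| Situation | 7.2 with the 6.8 prohibition, read literally | Other sections | Result |
|---|---|---|---|
| Rescue with non-study basal insulin | Leaves the study first | 6.1.3 and 6.8 Note: stays | Direct conflict |
| Permanent stop of study basal insulin for another reason, then non-study basal insulin | Leaves the study first | 7.1: stays | Direct conflict |
| Another glucose-lowering agent added while on study basal insulin | Leaves the study first | The stay-in-study sentences concern the basal insulin case or people who stopped study basal insulin | Unclear between sections; conflicts with the estimand |
| Short-term non-study insulin | Excepted in 6.8 | 7.1.3: visits continue | No conflict |

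The second row reaches beyond rescue, because under 7.1 every permanent discontinuer receives non-study basal insulin. In the third row the participant would not have been a retrieved dropout, so withdrawal adds a missing value without removing a donor.

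**Step 2. The plan's own figures.** Inputs from Protocol 9.1, 9.1.1 and 9.5: "The overall significance level (α) will be set to 0.05"; "The 2-sided 95% CI will be used for testing the noninferiority"; "The NIMs of 0.4% and 0.3% will both be tested to meet different regulatory requirements"; "Assuming an NIM of 0.4%, no true difference between treatment groups, and an SD of 1.1%, 568 completers".

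- Completers: 335 × 0.85 = 284.75 per arm; 568 / 0.85 gives 669 against about 670 stated.
- SE = 1.1 × √(2/284) = 0.0923.
- Power at margin 0.4: Φ(0.4/0.0923 − 1.96) = 99.1%.
- Power at margin 0.3: Φ(0.3/0.0923 − 1.96) = 90.1%.

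A noncentral t calculation also gives 99.1% and 90.1%. The stated figures reproduce, and nothing in 7.2 enters them.

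**Step 3. How close the fallback could be.** The documents give neither the share stopping treatment before Week 26 with a lasting switch nor the share of those still measured at Week 26. Both are assumptions here. With D treatment discontinuers per arm out of 335 and a share r still measured, the number of retrieved dropouts is taken as binomial(D, r), independently in each arm. The SAP keeps the retrieved-dropout method only if both arms reach 8, so the probability is P(X ≥ 8)².

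| Assumed to stop treatment | D per arm | r that gives 8 (8/D) | r = 10% | r = 20% | r = 30% | r = 50% |
|---|---|---|---|---|---|---|
| 5% | 17 | 47% | 0% | 0% | 1.1% | 47% |
| 10% | 34 | 24% | 0% | 13.5% | 71% | 99.9% |
| 15% | 50 | 16% | 1.5% | 65.5% | 98.6% | about 100% |

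The last four columns give the probability that both arms reach 8. If every site applied 7.2 to every switch to non-study basal insulin, r would be 0 and the fallback certain. The table shows sensitivity to retention. It does not estimate what 7.2 would cause.

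**The case against.** The strongest reply is that the basal insulin case is settled by specific text. Three places direct that the participant stays; the Note in 6.8 sits inside the prohibited list and qualifies it; and a treatment that 7.1 itself directs is hard to call prohibited. Reading 7.2 to cover every basal switch would leave 7.1 with no effect. The 7.2 list is also permissive in its opening, and the section expects withdrawal to be uncommon. SAP 1.2 states the intent to keep collecting HbA1c.

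Much of this stands. A careful site would probably follow the specific text. But the sentence inside the 7.2 item is directive and carries no exception. The amendment history lists 6.1.3 and the 6.8 Note as added in Amendment (a) with no listed change to 7.2, which is consistent with 7.2 not having been revisited but does not prove it. And if 7.2 is confined to other prohibited agents, it still ends HbA1c collection in people whose outcome the estimand counts.

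A reader might infer three stronger points that the documents do not support:

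- **That 6.1.3, 6.8 and 7.1 contradict 7.2 for any added glucose-lowering agent.** Their stay-in-study sentences follow the basal insulin case or concern people who stopped study basal insulin.
- **That the whole primary analysis changes when an arm has fewer than 8 retrieved dropouts.** Only the imputation of missing Week 26 values changes. Observed data, the ANCOVA and Rubin's rules stay, and the fallback is prespecified.
- **That a definite loss of power follows.** Any such figure needs a count of participants lost through 7.2, which the documents do not give. Placing retrieved dropouts on top of 15% missing would also misread Protocol 9.5, where the 15% are those who do not complete 26 weeks of treatment; retrieved dropouts belong within that group.

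**Conclusion.** The point holds as an inconsistency that works against the primary US analysis. For non-study basal insulin, 7.2 read literally with 6.8 conflicts with 6.1.3, the 6.8 Note and 7.1. For other glucose-lowering agents those sections leave the matter open, and the conflict is with an estimand defined regardless of rescue medication.

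The consequence is more missing Week 26 HbA1c and, for those who stopped study basal insulin, fewer retrieved dropouts. Its size cannot be computed: no rescue or retention rate is given, and rescue criteria apply only from Week 12. Under the illustrative assumption that 15% per arm stop treatment, the fallback is unlikely if 30% or more of them are still measured at Week 26 and likely if only 10% are. The stated sample size and power are not affected. The correction should be made because it is cheap and protects data that the treatment-regimen analysis relies on.

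**What to change.** Reconcile Protocol 7.2 with 6.1.3, 6.8 and 7.1 so that one rule applies to a participant who needs a prohibited effective agent, and say explicitly how non-study basal insulin and other glucose-lowering agents are each covered. Which treatment rule is kept is for the sponsor to decide.

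Separately from that rule, state in 7.2 that starting such an agent does not by itself end data collection, and that scheduled HbA1c at Weeks 26 and 52 continues for every participant who still consents.

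The cost is protocol wording and a clarification letter to sites. If Week 26 has already passed, report by arm how many participants left the study under this clause, so that its effect on missing data can be seen.
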